19.2 General Considerations

Statistical analysis of clinical endpoint data is the responsibility of the CTRU Statistician. A full statistical analysis plan will be written before any analyses are undertaken. The analysis plan will be written in accordance with current CTRU standard operating procedures and will be finalised and agreed by the following people: the trial statistician and supervising statistician, the Chief Investigator, the CTRU Delivery and Scientific Leads and the Senior Trial Manager. Any changes to the finalised analysis plan, and reasons for changes, will be documented.

All patients that receive at least one dose of Carfilzomib and with no protocol deviations with relevant impact on safety will be included in the safety analysis set.

The per protocol set will include all patients with at least one post baseline efficacy assessment who receive at least one dose of Carfilzomib and have no protocol deviations with relevant impact on efficacy.

Determination of the MTD in the dose escalation phase of the trial will be based on those patients who have received at least one cycle KTD and will be evaluated between the time of receiving the first dose of Carfilzomib in cycle 1 and the first dose of treatment in cycle 2. The safety review committee will review each DLT and attribute the DLT to the loading dose or the registered dose; any DLT attributed to the loading dose will be excluded when determining the MTD.

KTD Patients who do not receive one complete cycle due to experiencing a DLT will be included in the analysis; patients who do not receive at least one complete cycle for reasons other than toxicity, without experiencing a DLT, and who miss a dose of Carfilzomib, more than 14 doses Thalidomide or 2 doses of Dexamethasone in the first cycle, will be replaced. Evaluability will be considered by the safety review committee on an individual basis to account for attributing DLTs and missed doses to the loading or the registered dose.

The RD cohort will include all patients who are registered to receive and receive at least one dose of Carfilzomib at the RD. This cohort will include patients from the dose escalation and dose expansion phases of the study. All patients who do not fulfil these criteria will be included in the non-RD cohort.

Statistical analysis will be descriptive for all endpoints, and will be summarised overall and by dose cohort. All safety analyses will be based upon the safety analysis set; safety data from patients not included in this analysis set will be listed separately. All efficacy analyses will be based upon the per protocol set. Patients who do meet the criteria to be included in each of analysis sets will have the reasons for emission listed. A sensitivity analysis on the efficacy endpoints may be considered if the total number of patients in each of the analysis sets differs by more than 3 patients.

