Statistical summary:	
Sample Size
 
In the dose escalation phase of this study, a minimum of 6 (3 at dose level 0 and 3 at dose level -1) and a maximum of 18 (6 at dose level 0, 1, and 2) patients will be recruited in a 3+3 design with cohorts of between 3 and 6 patients, in order to determine maximum tolerated dose (MTD) and recommended dose (RD). At the recommended dose level identified, a further 20 patients will be recruited to further assess safety and toxicities at the RD.
 
Analysis sets and dose cohorts
 
All patients that receive at least one dose of Carfilzomib will be included in the safety analysis set.
 
The per protocol analysis set will include all patients with at least one post baseline efficacy assessment who receive at least one dose of Carfilzomib and have no protocol deviations with relevant impact on efficacy.
 
Determination of the MTD in the dose escalation phase of the trial will be based on those patients who have received at least one cycle KTD and will be evaluated between the time of receiving the first dose of Carfilzomib in cycle 1 and the first dose of treatment in cycle 2. The safety review committee will review each DLT and attribute the DLT to the loading dose or the registered dose; any DLT attributed to the loading dose will be excluded when determining the MTD. KTD Patients who do not receive one complete cycle due to experiencing a DLT will be included in the analysis; patients who do not receive at least one complete cycle for reasons other than toxicity, without experiencing a DLT, and who miss a dose of Carfilzomib, more than 14 doses of Thalidomide or 2 doses of Dexamethasone in the first cycle, will be replaced. Evaluability will be considered by the safety review committee on an individual basis to account for attributing DLTs and missed doses to the loading or the registered dose. The RD cohort will include all patients who are registered to receive and receive at least one dose of Carfilzomib at the RD. This cohort will include patients from the dose escalation and dose expansion phases of the study. All patients who do not fulfill this criteria will be included in the non-RD cohort.
 
All safety analyses will be based upon the safety analysis set; safety data from patients not included in this analysis set will be listed separately. All Efficacy analyses will be based upon the per protocol set.
 
Primary endpoints and analysis
 
The number of patients experiencing DLTs within the first cycle of KTD will be presented, with descriptive summaries of the specific DLTs observed. Summaries will be presented for each dose level. This data will be presented for patients registered to the dose escalation phase of the study only.

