13.2 Reporting Procedures

13.2.1 All Adverse Events (AEs)

All adverse events that occur between informed consent and 30 days post last trial treatment administration must be recorded in the patient notes and the trial CRFs. Those meeting the definition of a Serious Adverse Event (SAE) must also be reported to LEEDS CTRU within 24 hours of becoming aware of the event using the trial specific SAE Report. Also refer to section 13.2.2 (Serious Adverse Events (SAEs)).

Pre-existing conditions do not qualify as adverse events unless they worsen.

Overdoses

All accidental or intentional overdoses, whether or not they result in adverse events, must be recorded in the patient notes and CRFs. Overdoses resulting in an adverse event are classified as SAEs and must be reported to LEEDS CTRU according to SAE reporting procedures. The fact that an overdose has occurred must be clearly stated on the SAE Report. Also refer to section 13.2.2 (Serious Adverse Events (SAEs)).

Sites must inform LEEDS CTRU immediately when an overdose has been identified. Also refer to section 17 (Incident Reporting and Serious Breaches).

Adverse Event Term

An adverse event term needs to be provided for each adverse event, preferably using the term listed in the Common Terminology Criteria for Adverse Events (CTCAE) version 4.03, available online at: http://evs.nci.nih.gov/ftp1/CTCAE/CTCAE_4.03_2010-06-14_QuickReference_8.5x11.pdf

Severity

Severity for each adverse event will be determined by using the Common Terminology Criteria for Adverse Events (CTCAE) version 4.03 as a guideline, wherever possible. The criteria are available online at: http://evs.nci.nih.gov/ftp1/CTCAE/CTCAE_4.03_2010-06-14_QuickReference_8.5x11.pdf. Appendix 5 also details some toxicity criteria.

In those cases where the CTCAE criteria do not apply, severity should be coded according to the following criteria:

- 1 = Mild (awareness of sign or symptom, but easily tolerated)
- 2 = Moderate (discomfort enough to cause interference with normal daily activities)
- 3 = Severe (inability to perform normal daily activities)
- 4 = Life threatening (immediate risk of death from the reaction as it occurred)
- 5 = Fatal (the event resulted in death)

Causality

The PI, or other delegated site investigator, must perform an evaluation of causality for each adverse event. Causal relationship to each trial treatment must be determined as follows:

- **None**
There is no evidence of any causal relationship.
- **Unlikely**

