Where central monitoring of data and/or documentation submitted by sites indicates that a patient may have been placed at risk (e.g. evidence of an overdose having been administered, indication that stopping rules for an IMP were not observed following an adverse reaction, etc.), the matter will be raised urgently with site staff and escalated as appropriate (refer to section 17 (Incident Reporting and Serious Breaches) and 16.2 ('For cause' on-site monitoring) for further details).

16.2 'For Cause' On-Site Monitoring

On-site monitoring visits may be scheduled where there is evidence or suspicion of non-compliance at a site with important aspect(s) of the trial protocol/GCP requirements. Sites will be sent a letter in advance outlining the reason(s) for the visit. The letter will include a list of the documents that are to be reviewed, interviews that will be conducted, planned inspections of the facilities, who will be performing the visit and when the visit is likely to occur.

Following a monitoring visit, the Trial Monitor/Trial Coordinator will provide a report to the site, which will summarise the documents reviewed and a statement of findings, deviations, deficiencies, conclusions, actions taken and actions required. The PI at each site will be responsible for ensuring that monitoring findings are addressed in a timely manner, and by the deadline specified.

LEEDS CTRU will assess whether it is appropriate for the site to continue participation in the trial and whether the incident(s) constitute a serious breach. Refer to section 17 (Incident Reporting and Serious Breaches) for details.

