18.0 Endpoints

18.1 Primary endpoints

Dose-Limiting Toxicities (Dose escalation phase), between the time of receiving the first registered dose of Carfilzomib in cycle 1 and day 1 cycle 2, in order to establish the Maximum Tolerated Dose (MTD) and recommended dose (RD) of Carfilzomib in combination with Thalidomide and Dexamethasone.

Proportion of patients treated who experience any grade 3 or 4 CTCAE toxicity throughout all treatment cycles

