3.2 Safety analysis set

All patients that receive at least one dose of Carfilzomib and with no protocol deviations with relevant impact on safety will be included in the safety analysis set.

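### The safety set in Protocol 19.2 and the SAP can drop treated patients for undefined deviations, against the synopsis and a primary toxicity rate defined on treated patients

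*Protocol*

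**What the plan says.** **Safety set.** The statistical summary in Protocol 1.1 reads: "All patients that receive at least one dose of Carfilzomib will be included in the safety analysis set". Protocol 19.2 adds a condition: "All patients that receive at least one dose of Carfilzomib and with no protocol deviations with relevant impact on safety will be included". SAP 3.2 carries the same condition, so that only dosed patients "with no protocol deviations with relevant impact on safety will be included in the safety analysis set".

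**Where it is used.** Protocol 19.2 says: "All safety analyses will be based upon the safety analysis set; safety data from patients not included in this analysis set" go into a separate listing. The introduction to SAP section 3 agrees. SAP 5.1 makes the relevant analysis population the denominator for percentages.

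**Endpoint.** The second primary endpoint (Protocol 18.1, SAP 2.1) is: "Proportion of patients treated who experience any grade 3 or 4 CTCAE toxicity throughout all treatment cycles".

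**Efficacy.** The synopsis says: "All Efficacy analyses will be based upon the per protocol set". Under Protocol 19.2 and SAP 3.3, that set requires a carfilzomib dose, an efficacy assessment after baseline, and no deviation bearing on efficacy. A sensitivity analysis is optional and depends on the set sizes differing by more than 3.

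**Cohorts.** Protocol 19.2 and SAP 3.5 place in the RD cohort patients who were both registered to the RD and dosed at it; everyone else is non-RD. SAP 5.1 describes the non-RD population as escalation-phase patients treated at other levels. Protocol 8.1.1 gives 20 mg/m² on cycle 1 day 1 and the RD only from day 8.

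**The concern.** The expansion phase exists to describe toxicity at the RD and to give a first look at activity. A safety set normally holds everyone exposed, because a deviation in how the drug was given is part of what happened to the patient. Here an analyst following Protocol 19.2 and the SAP would remove treated patients on a criterion with no list of qualifying deviations, no named decision-maker and no time point. In an open-label trial, that leaves room to decide exclusions with outcomes in view.

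The removal affects the primary grade 3 or 4 rate and also the SAE and maximum-grade tables in SAP 5.3.2. A listing discloses the excluded patient but does not put that patient back into the rate.

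The efficacy set raises a similar question, because treated patients with no assessment after baseline leave the denominator of the response rate.

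**Working it through.** **1. Planned numbers.** Protocol 19.1 gives an escalation minimum of 3 + 3 = 6, a maximum of 3 × 6 = 18, and 20 more at the RD; these reproduce. Table 2 in Protocol 8.1.3 requires at least 6 patients to complete cycle 1 at the RD before expansion. The planned RD cohort is therefore 6 + 20 = 26, and the planned maximum overall is 18 + 20 = 38.

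**2. Which denominator applies.** Protocol 18.3 and SAP 2.3.1 describe the toxicity proportion as a count and name no denominator. Protocol 19.2 sends all safety analyses to the safety set, and SAP 5.1 makes that population the denominator. An excluded treated patient therefore leaves both numerator and denominator.

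**3. Effect on the toxicity rate.** The documents give no expected rate and no number of exclusions, so both are assumed. With x events among n treated and k excluded, the reported rate lies between (x − k)/(n − k), if all excluded patients had events, and x/(n − k), if none did.

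| Treated | Excluded | All excluded had events | None had events |
|---|---|---|---|
| 10/26 = 38.5% | 1 | 9/25 = 36.0% | 10/25 = 40.0% |
| 10/26 = 38.5% | 2 | 8/24 = 33.3% | 10/24 = 41.7% |
| 10/26 = 38.5% | 3 | 7/23 = 30.4% | 10/23 = 43.5% |
| 8/26 = 30.8% | 3 | 5/23 = 21.7% | 8/23 = 34.8% |
| 13/26 = 50.0% | 3 | 10/23 = 43.5% | 13/23 = 56.5% |
| 18/26 = 69.2% | 3 | 15/23 = 65.2% | 18/23 = 78.3% |
| 15/38 = 39.5% (overall) | 3 | 12/35 = 34.3% | 15/35 = 42.9% |

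The exact (Clopper-Pearson) 95% interval for 10/26 is 20.2% to 59.4%, so both ends of the three-exclusion range lie well inside it.

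**4. Effect on response.** Assume 13 responders among 26 treated, 50.0% (95% interval 29.9% to 70.1%). Dropping 1, 2 or 3 unassessed patients, who would otherwise count as non-responders, gives 13/25 = 52.0%, 13/24 = 54.2% or 13/23 = 56.5%. In the last case the sets hold 26 and 23. The difference is 3, which is not more than 3, so even the optional sensitivity analysis is not prompted. Because the trigger compares sizes, exclusions from both sets can also cancel: 3 out of one and 3 others out of the other leave 23 and 23.

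The efficacy-deviation clause has no fixed direction. With 3 patients dropped in all, of whom 0, 1, 2 or 3 are responders, the rate is 13/23 = 56.5%, 12/23 = 52.2%, 11/23 = 47.8% or 10/23 = 43.5%.

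**5. Cohort rules.** Take an expansion patient who receives only the day-1 loading dose.
- Under SAP 3.5 the patient is non-RD, having had no dose at the RD.
- Under SAP 5.1 the patient is RD if treatment at a dose means the assigned level. Otherwise the patient is in neither group, because non-RD there is confined to the escalation phase.

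Either reading disagrees with 3.5. If one such patient had grade 3 toxicity and the RD rate would otherwise be 11/26 = 42.3%, it becomes 10/25 = 40.0% under 3.5. The event stays in the overall summary.

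**The case against.** **One operative rule.** Protocol 19.2 and SAP 3.2 agree, so the analyst is not left choosing, and excluded patients are disclosed in a listing. This is true, but the SAP's own endpoint is a proportion of treated patients, so the rule conflicts with the quantity it is meant to estimate. SAP 3.1 keeps patients later found ineligible, as appropriate; that covers only one kind of deviation.

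**Hidden toxicity.** A reader might infer that the plan understates toxicity by removing patients harmed by dosing errors. Protocol 16.1 gives as signals of risk "evidence of an overdose having been administered, indication that stopping rules for an IMP were not observed following an adverse reaction", and Protocol 13.2.1 says "Overdoses resulting in an adverse event are classified as SAEs". Those sections concern monitoring and reporting, and neither links such patients to exclusion from an analysis set. The nearest pointer is SAP 4.2, which uses first-cycle drug compliance to confirm the analysis sets. That points at least as readily to missed doses, and excluding under-dosed patients would tend to raise the rate. The direction is therefore open. What stands is that the clause is undefined and could reach either kind of patient.

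**Inflated response.** A reader might also infer that every missing response leaves the denominator. SAP 5.1 keeps per-protocol patients with missing data in it, and Protocol 14.1.1 keeps patients who stop treatment for clinical reasons in follow-up. Only treated patients with no assessment after baseline are dropped on that ground. How many that is depends on what counts as post-baseline, and it could be very few, since samples are also scheduled on cycle 1 day 1.

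**Fatal toxicity.** The grade 3 or 4 wording does not make deaths disappear. Maximum-grade toxicity, SAEs by seriousness and deaths at 6 months are all summarised.

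**Consequence.** The analysis is descriptive, with no test and no decision rule on the toxicity rate. This limits the severity, and it stands.

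**Conclusion.** The contradiction over the safety set is real and should be fixed. Protocol 19.2 and SAP 3.2 allow treated patients to be left out of a primary toxicity rate defined on treated patients, for deviations that neither document defines. On assumed counts (26 at the RD, 10 events, 3 exclusions) the reported rate could lie anywhere from 30.4% to 43.5% instead of 38.5%. That is within sampling error, and the sign of the bias cannot be predicted.

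It would be wrong to conclude that the MTD or RD is compromised. Dose selection has its own evaluability rule (Protocol 19.2, SAP 3.4) and does not use the safety set.

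The efficacy point is secondary. Compared with counting unassessed treated patients as non-responders, dropping them can only raise the response rate (50.0% to 56.5% for three, on assumed counts). The deviation clause can move the rate either way, so net inflation is not established.

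The disagreement between SAP 3.5 and 5.1 is minor. It concerns the rare expansion patient who receives only the loading dose, and it does not show that such a patient necessarily has no place in the tables.

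**What to change.** 1. In Protocol 19.2 and SAP 3.2, define the safety set as every patient given any carfilzomib, with deviations flagged and not used for exclusion. This matches the synopsis and the endpoint.
2. In Protocol 1.1 and 19.2, and in the introduction to SAP section 3 and SAP 3.3, always report response in all treated patients, with unassessed patients counted as non-responders, alongside the per-protocol result. Delete the trigger based on a difference of more than 3 patients.
3. Reconcile SAP 3.5 with SAP 5.1 so that each treated patient falls in exactly one cohort. Also report the toxicity rate by registered dose level among all treated patients.

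The cost is a wording amendment to the protocol (through Protocol 21.4) and the SAP, plus one or two extra tables. No new data are needed. Response may read slightly less favourably, and the toxicity rate may move either way.

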19.3 Primary Endpoint Analysis

The number of patients experiencing DLTs within the first cycle of KTD will be presented, with descriptive summaries of the specific DLTs observed. Summaries will be presented for each dose level. This data will be presented for patients registered to the dose escalation phase of the study only.

Further summaries of longer-term tolerability will also be presented for patients registered to the dose escalation phase to include the maximum toxicity grade experienced within the first three cycles of treatment, overall and by cycle. Individual listings of the toxicities, grade and cycle of all toxicities experienced within the first three cycles will be presented.

The number of patients experiencing any grade 3 or 4 CTCAE toxicity within all cycles of treatment will be summarised. This will be presented overall and by dose cohort, across all cycles as well as by each cycle.

19.4 Secondary Endpoint Analysis

Safety and toxicity profiles for each cycle and cohort: data will be summarised descriptively, including the proportion of patients experiencing at least one SAE, the number of SAEs experienced per participant, and the number of SAEs experienced according to seriousness criteria, causality, and body system; Toxicity will be summarised according to CTCAE grades and will be summarised as the maximum grade toxicity experienced within each cycle, and overall.

The proportion of patients achieving at least a PR (clonal response) within 3m, at 3m, within 6m and at 6m and the proportion of patients achieving an amyloidotic organ response within 3m and 6m will be presented in tabulated form. Corresponding 90% and 95% confidence intervals will also be presented. Responses at 3 and 6 months will be broken down by response achieved, and by organ (for organ response).

Time to amyloidotic organ response and time to maximum response will be calculated using the Kaplan Meier method. Median time to amyloidotic organ response and median time to maximum response will be presented, with corresponding 95% confidence intervals.

The proportion and number of patients alive at 6 months and patients progression free at 6months will be presented with corresponding 90% and 95% confidence intervals. If the data warrants Kaplan Meier curves for progression free survival may be explored.

Each patient will be assessed for their maximum clonal response; the number and proportion of participants in each response category within 6 cycles of treatment will be presented with corresponding 95% confidence intervals. Patients who do not achieve a maximum response will be summarised as, “no maximum response”.

Feasibility of delivering treatment according to protocol schedule will be summarised descriptively to include the number of patients requiring dose delays and/or reductions, the number of patients withdrawing from treatment, and reasons for dose delays / reductions and withdrawals. Time on treatment and reasons for stopping treatment will also be presented. The number of doses missed will be summarised overall and by cycle.

The following definitions will be used:

$\% \text{ of intended dose} = 100 * (\text{dose received} / \text{planned dose})$

To represent delays in cycles and reduced dose:

$\text{Dose intensity (DI)} = \text{Cumulative Dose} / \text{Duration}$

$\text{Relative Dose intensity (RDI)} = \text{Actual DI} / \text{Planned DI}$

Summaries will be produced at each cycle, for each treatment and overall.

19.5 Frequency of Analyses

During the Dose Escalation Phase, recruitment will be halted after each group of three patients have completed at least one cycle of KTD, to allow safety data to be assessed. CTRU will produce a summary of DLTs at each dose level, detailed safety listings, and recruitment figures for consideration by the Safety Review Committee.

No formal analyses are planned until after the trial is closed to recruitment and the required number of patients has been recruited. Final analysis will be carried out when the required number of patients has been recruited and all patients have been followed up for at least 6 months from registration.

